## **5 Statistical methods for Pharmacokinetic (PK) parameters**

### **5.1 Variables**

The parent compound QBW276 and the hydrolysis products QBP545 and QBV697 will be determined in whole blood.

The following pharmacokinetic parameters for all three analytes will be determined for Day 1 and Day 7 or 14 in Cohorts 1 and 2 using the actual recorded sampling times and noncompartmental methods: Cmax, Tmax, and AUCtau on Day 1 and Cmax,ss, Tmax,ss, and AUCtau,ss on Day 7 for cohort 1 and Day 14 for cohort 2. Half-lives will be calculated by log-linear regression on the terminal portion of the concentration-time profile if enough concentrations are available (minimum 3). Racc will be derived as the ratio of AUCtau,ss from Day 14 divided by the AUCtau from Day 1.

In cohort 3, exposure from 15-minute sample after start of inhalation of the morning dose on selected days will be monitored.

Other PK parameters maybe calculated in all cohorts if deemed necessary.

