as long as the systemic exposure cap based on pre-clinical data or a clinical maximum tolerated dose (MTD) is not exceeded. Cohorts 1 and 2 will enroll 8 patients each, with 6 patients randomized to receive active drug and 2 patients randomized to receive matching placebo. Cohort 1 will be dosed for 1 week while cohort 2 will be dosed for 2 weeks. Cohort 2 will be initiated only after cohort 1 has completed dosing. Cohort 2 may be skipped if safety, tolerability, PK and PD data from cohort 1 are found favorable to proceed directly to cohort 3. In cohorts 1 and 2, patients may be replaced if they do not complete the study duration for reasons other than safety to obtain 8 completers in each cohort. If a patient has participated in cohort 1, he/she may qualify to participate in cohort 2 contingent upon approval from the sponsor, as long as he/she has been through a 4 week wash-out between dosing in the two cohorts, and has not experienced any significant AEs since enrollment in cohort 1. This will ensure that no patient receives more than 4 weeks of the investigational drug QBW276 in his/her lifetime until further supportive toxicology studies are conducted in the drug's development program.

NOTE: No patient randomized to cohort 1 or 2 will be eligible for cohort 3.

Cohort 1 and 2

Cohorts 1 and 2 will consist of a 21 day screening period followed by a baseline visit and a 7 or 14 day Treatment Period in cohort 1 and 2, respectively. Adequate windows will be provided for patient's convenience. QBW276 will be administered on top of the patient's usual standard of care medications.

Study inclusion/exclusion criteria as well as medication use will be assessed at screening. Patients who meet the inclusion/exclusion criteria at screening will report to the study site on Day -1 at a time specified by the investigator, for the baseline assessments. All baseline safety evaluation results must be available prior to dosing on Day 1, hence, Day -1 assessments can be carried out up to 72 hours prior to Day 1 dosing.

Patients who meet all of the inclusion and none of the exclusion criteria at baseline will then report to the study site on Day 1 and will remain in the clinic until at least 6 hours after the first dose in the morning.

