8.5 Pharmacokinetics

Pharmacokinetic blood samples will be collected at the time points defined in the [Assessment schedule](#). In Cohorts 1 and 2 this consists of multiple samples through 6 hours after inhalation on Days 1 and either 7 or 14 and predose concentrations on selected days. In Cohort 3 this consists of a 15-minute sample after the start of inhalation of the morning dose on selected days. Details on sample collection, numbering, processing and shipment are in the SOM. The customized tubes used for collection of PK blood samples are not sterile and must NOT be filled by direct phlebotomy; the specific instructions on the use of these tubes, provided in the SOM, must be followed.

Corporate Confidential Information

Concentrations below the quantification limit will be reported as 0 ng/mL. Blood remaining after completion of the bioanalytics described above may be used for exploratory assessment of metabolites or other bioanalytical purposes (e.g. cross check between different sites, stability assessment).

Pharmacokinetic abbreviations and definitions are in the list at the beginning of this protocol. The following pharmacokinetic parameters for all three analytes will be determined for Day 1 and Day 7 or 14 in Cohorts 1 and 2 using the actual recorded sampling times and noncompartmental methods: Cmax, Tmax, and AUCtau on Day 1 and Cmax,ss, Tmax,ss, and AUCtau,ss on Day 7 for cohort 1 and Day 14 for cohort 2. Half-lives will be calculated by log-linear regression on the terminal portion of the concentration-time profile if enough concentrations are available (minimum 3). Racc will be derived as the ratio of AUCtau,ss from Day 14 divided by the AUCtau from Day 1. In cohort 3, exposure from 15-minute sample after start of inhalation of the morning dose on selected days will be monitored. Other PK parameters may be calculated in all cohorts if deemed necessary.

In order to avoid long clinical stays for patients in this study, the blood sampling for AUC's is terminated at 6 hours after inhalation.

Corporate Confidential Information

Corporate Confidential Information

No formal statistical comparison is foreseen as the intent of this comparison is to determine if exposure is similar in the two groups.

Corporate Confidential Information

Corporate Confidential Information

9 Safety monitoring

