### 5.2.1 Statistical model, assumptions and hypotheses

An exploratory statistical analysis analysis of the accumulation ratio of Day 7 vs Day 1 for cohort 1, Day 14 vs Day 1 for cohort 2 and Day 28 vs Day 1 for cohort 3 may be carried out for the parameters AUCtau and Cmax for each dose level. A mixed linear model will be fitted to the log-transformed observations. This model will include day as a factor ("Day 7/14/28" and "Day 1"), log-dose as a covariate, and subject as a random effect. The mean difference between Day 7/14/28 and Day 1 for each dose-level, together with 90% confidence limits, will be calculated from this model. These will be back-transformed to provide an estimate of the accumulation ratio (Day 7/14/28 vs. Day 1) with corresponding 90% CI for both parameters. Due to the small number of subjects in cohorts 1 and 2 there may be convergence issues with the mixed model. In case of convergence issues, alternative covariance structures will be considered and compared using standard fit statistics (AIC).

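### Racc is fixed at Day 14 over Day 1 in Protocol 8.5 and SAP 5.1, so the patient-level ratio cannot be derived for Cohort 1, whose steady-state profile is on Day 7

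*SAP*

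**What the plan says.** Protocol 8.5 and SAP 5.1 list the non-compartmental parameters for Cohorts 1 and 2. Both put the steady-state AUC at a different day in each cohort: "AUCtau,ss on Day 7 for cohort 1 and Day 14 for cohort 2". Later in the same paragraph both define the accumulation ratio with one fixed day: "Racc will be derived as the ratio of AUCtau,ss from Day 14 divided by the AUCtau from Day 1". The SAP was built on protocol v02 and the current protocol is v04, but the sentence is the same in both documents, so this is not a version difference.

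On duration, Protocol 3.1 says "Cohort 1 will be dosed for 1 week while cohort 2 will be dosed for 2 weeks". It also says "Cohort 2 may be skipped if safety, tolerability, PK and PD data from cohort 1 are found favorable to proceed directly to cohort 3".

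SAP 5.2.1 handles accumulation differently. It describes an exploratory mixed model and names its targets by cohort: "accumulation ratio of Day 7 vs Day 1 for cohort 1, Day 14 vs Day 1 for cohort 2 and Day 28 vs Day 1" (the last pair belongs to Cohort 3). This analysis "may be carried out for the parameters AUCtau and Cmax for each dose level".

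For Cohort 3 sampling, Protocol 8.5 says "In Cohort 3 this consists of a 15-minute sample after the start of inhalation of the morning dose on selected days".

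**The concern.** The numerator of Racc is tied to a day that one of the two profiled cohorts does not have. Protocol 11.4.2 and SAP 5.2 send the reader back to Protocol 8.5 and SAP 5.1 for the parameters to be listed by patient and summarised. A programmer who follows those sections literally would produce no individual Racc and no Racc summary for Cohort 1.

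PK is part of the primary objective in Cohorts 1 and 2, and Cohort 1 gives the first repeated-dose exposure data in patients in this study. A ratio of steady-state to first-dose exposure is a natural summary of those data, and SAP 5.2.1 shows that a Day 7 ratio was in mind for this cohort. What is at stake is a complete and consistent PK report, most of all if Cohort 2 is not run.

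**Working it through.** The plan gives no figure for Racc, so the check is a cross-reading and a count.

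**Inputs**
- Racc numerator and denominator: Protocol 8.5 and SAP 5.1.
- Visits: Protocol Table 8-1. Cohort 1 attends on Days 1, 2 and 7, with end of study on Day 11 (±2). Cohort 2 has Days 1, 2, 7 and 14, with end of study on Day 18 (±2).
- Active patients: 6 of 8 in each of Cohorts 1 and 2 (Protocol 3.1 and 6.2).
- Cohort 3 PK: one 15-minute sample per sampling day (Protocol 8.5 and Table 8-1).

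The count of 6 agrees with the adverse-event probabilities in Protocol 11.6. With n = 6 and incidence 23.5%, P(at least one) = 1 − 0.765^6 = 0.7996 (stated 80%). P(two or more) = 1 − 0.765^6 − 6 × 0.235 × 0.765^5 = 0.4301 (stated 43%). With n = 8 the values are 0.8827 and 0.5944, which do not match.

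**Side by side**

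| Cohort | Planned active | Days with an AUCtau | Racc as worded | Ratio named in SAP 5.2.1 (optional) |
|---|---|---|---|---|
| 1 | 6 | 1 and 7 | Not derivable: no Day 14 profile | Day 7 / Day 1, estimable |
| 2 | 6 | 1 and 14 | Derivable | Day 14 / Day 1, estimable |
| 3 | crossover | none | Not derivable: no AUCtau | Day 28 / Day 1, not estimable for AUCtau or Cmax |

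**Count, both cohorts run.** Active patients planned = 6 + 6 = 12. Without a defined Racc = 6, and 6/12 = 50%. A Cohort 1 patient may re-enter in Cohort 2 with sponsor approval after a washout. That does not supply the missing ratio, because Cohort 2 starts from its own Day 1 and is listed at a different dose level.

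**Count, Cohort 2 skipped.** Patients with the defined Racc = 0. The components of a Day 7 / Day 1 ratio still exist for all 6 planned active patients in Cohort 1.

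**Cohort 3 as a substitute.** One concentration at 15 minutes gives neither an AUC over the dosing interval nor an observed maximum. Only a ratio of 15-minute concentrations can be formed. The Day 28 entry in SAP 5.2.1 therefore does not fill the gap.

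**What SAP 5.2.1 supplies.** For Cohort 1 it gives a model-based mean ratio by dose level: "These will be back-transformed to provide an estimate of the accumulation ratio (Day 7/14/28 vs. Day 1) with corresponding 90% CI for both parameters". It does not give a ratio per patient, its conduct is discretionary, and the SAP itself warns that the model may not converge in the small cohorts.

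**The case against.** The strongest reply is that this is a drafting slip with little consequence. The Day 7 / Day 14 split by cohort stands in the same paragraph and is carried through in SAP 5.2.1, so the intent is clear. Both component AUCs are required for Cohort 1 and listed by patient, which leaves Racc one division away. Both documents also allow further PK parameters where they are judged necessary. All of this stands, and it is why the point is small. It does not make the definition correct: the sentence that governs the listings still names a day that Cohort 1 lacks, and every route around it is discretionary.

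A reader might infer two stronger points, and the documents support neither.

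- *That skipping Cohort 2 leaves the trial with no accumulation ratio at all.* SAP 5.2.1 names a Day 7 versus Day 1 ratio for Cohort 1, for AUCtau and Cmax, with a 90% interval. Optional is not absent.
- *That the dose decisions depend on the missing ratio.* Protocol 7.5(c) compares observed or predicted mean systemic exposure with a preclinical limit, and the visible part of 3.3 asks for an exposure margin after each cohort. Neither mentions Racc, and the Day 7 steady-state AUC, which is fully defined, is available to both. Parts of 3.3 are redacted, so reliance on Racc there cannot be shown.

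The primary-endpoint argument also has limits. The endpoint tables list PK measurements in general, and Protocol 11.4.1 names adverse-event occurrence as the primary variable for Cohorts 1 and 2. No visible hypothesis or threshold uses Racc.

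**Conclusion.** The definition is wrong as written in both documents and disagrees with SAP 5.2.1. The patient-level Racc cannot be derived for Cohort 1, which is 6 of the 12 planned active patients. If Cohort 2 is skipped, no patient has it, and the only AUC-based accumulation estimate left is an optional model.

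The effect is on the completeness and consistency of the PK outputs. No data are lost and no effect on the exposure checks is shown, so this is a minor correction.

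The counts assume planned enrolment with evaluable profiles in every active patient. The conclusion also assumes that no redacted text in Protocol 8.5 gives a separate Day 7 definition. If one existed, the visible sentence would still need to agree with it.

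**What to change.** In Protocol 8.5 and SAP 5.1, define Racc as AUCtau,ss (Day 7 in Cohort 1, Day 14 in Cohort 2) divided by AUCtau on Day 1, listed by patient and summarised by cohort. This brings both sections into line with the Cohort 1 and Cohort 2 ratios in SAP 5.2.1.

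While SAP 5.2.1 is open, state that the Cohort 3 comparison of Day 28 with Day 1 can use only the 15-minute concentrations, since AUCtau and Cmax are not available there.

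The cost is one phrase in each document plus a clarifying line in SAP 5.2.1. No new samples, visits or patients are needed.

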## 5.2 Descriptive analyses

The concentrations will be listed by treatment, patient and visit/sampling time point. Descriptive statistics will be provided by treatment and visit/sampling time point. Summary statistics will include mean (arithmetic and geometric), SD, and CV (arithmetic and geometric), median, minimum and maximum.

Concentrations below the LLOQ will be treated as zero in summary statistics. A geometric mean and CV will not be reported if the dataset includes zero values.

Pharmacokinetic parameters in Cohorts 1 and 2 will be calculated as described in Section 5.1 and will be listed by treatment and patient. Descriptive summary statistics will include mean (arithmetic and geometric), SD, and CV (arithmetic and geometric), median, minimum and maximum. An exception to this is Tmax and Tmax,ss where median, minimum and maximum will be presented.

### 5.2.1 Statistical model, assumptions and hypotheses

An exploratory statistical analysis analysis of the accumulation ratio of Day 7 vs Day 1 for cohort 1, Day 14 vs Day 1 for cohort 2 and Day 28 vs Day 1 for cohort 3 may be carried out for the parameters AUCtau and Cmax for each dose level. A mixed linear model will be fitted to the log-transformed observations. This model will include day as a factor ("Day 7/14/28" and "Day 1"), log-dose as a covariate, and subject as a random effect. The mean difference between Day 7/14/28 and Day 1 for each dose-level, together with 90% confidence limits, will be calculated from this model. These will be back-transformed to provide an estimate of the accumulation ratio (Day 7/14/28 vs. Day 1) with corresponding 90% CI for both parameters. Due to the small number of subjects in cohorts 1 and 2 there may be convergence issues with the mixed model. In case of convergence issues, alternative covariance structures will be considered and compared using standard fit statistics (AIC).

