	Visit Name	Screening	Baseline	Day 1	Day 7	Day 14	Day 21	Day 28	Washout	Baseline/ET/EOS ²	Day 57	Day 63	Day 70	Day 77	Day 84	ET/EOS
Visit Numbers ¹	1	2	101	103	104	105	106		199	201	202	203	204	205	299	
Study Day(s)	-45 to -14	-7 to -4	1	7 -2 +2	14 -2 +2	21 -2 +2	28 -2 [contact] -0 +2	57	63 -2 +2	70 -2 +2	77 -2 +2	84 -2 +0	91 -3 +3	
Study Drug Questionnaire									X ¹³							X
Phase / Study completion information		X ¹¹							X ¹³							X

¹ Visit structure given for internal programming purpose only

² Baseline: For patients continuing onto study treatment period 2.

ET/EOS: Early Termination/End of Study: For subjects who undergo study/treatment discontinuation and subjects who withdraw prematurely

³ Telephone Contact on Day 42 (-5/+5) of Washout

⁴ Pre-dose

Corporate Confidential Information

⁶ Central lab collection: Sodium, potassium, bicarbonate, creatinine, BUN, uric acid, chloride, albumin, calcium, alkaline phosphatase, total bilirubin, LDH, GGT, AST, ALT, PT/INR, amylase, lipase, CK, glucose, total cholesterol, and triglycerides

⁷ Serum pregnancy test

⁸ Urine pregnancy test. If positive, drug must be withheld and a confirmatory serum pregnancy test must be sent

⁹ PK blood sample to be collected at 15 minutes after the start of inhalation of the morning dose

¹⁰ Randomization can occur any time between visits 2 and 101 after eligibility is confirmed

¹¹ Screening phase completion

¹² To be completed only for Baseline visit

¹³ To be completed only for ET/EOS (Early Termination/End of Study) visit

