11.5.3 Pharmacokinetics

The 15 minute post-dose concentrations in Cohort 3 will be listed by treatment, patient and visit/sampling time point. Descriptive statistics will be provided by treatment and visit/sampling time point. Summary statistics will include mean (arithmetic and geometric), SD, and CV (arithmetic and geometric), median, minimum and maximum. Concentrations below the LLOQ will be treated as zero in summary statistics. A geometric mean will not be reported if the dataset includes zero values.

Corporate Confidential Information

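### The accumulation-ratio model in SAP 5.2.1 yields one common ratio rather than one per dose level, and it asks for cohort 3 parameters that the sampling cannot supply

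*SAP*

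**What the plan says.** SAP 5.2.1 allows an exploratory analysis of accumulation: Day 7 against Day 1 in cohort 1, Day 14 against Day 1 in cohort 2, and "Day 28 vs Day 1 for cohort 3 may be carried out for the parameters AUCtau and Cmax for each dose level". The response is log-transformed. Day enters as a factor with two named levels, one of them the combined Day 7/14/28 and the other Day 1. The remaining terms are "log-dose as a covariate, and subject as a random effect". No interaction is listed. The promised output is: "The mean difference between Day 7/14/28 and Day 1 for each dose-level, together with 90% confidence limits, will be calculated from this model". The differences are then back-transformed to accumulation ratios.

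Protocol 6.2 sets 3 mg bid for cohort 1, 6 mg bid for cohort 2, and a dose of no more than 6 mg bid for cohort 3. Cohorts 1 and 2 each enrol 8 patients, "with 6 patients randomized to receive active drug and 2 patients randomized to receive matching placebo" (protocol 3.1).

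On cohort 3 sampling, protocol 8.5 says: "In Cohort 3 this consists of a 15-minute sample after the start of inhalation of the morning dose on selected days". The cohort 3 footnote to protocol Table 8-1 agrees: "PK blood sample to be collected at 15 minutes after the start of inhalation of the morning dose". Protocol 11.5.3 summarises only that measurement: "The 15 minute post-dose concentrations in Cohort 3 will be listed by treatment, patient and visit/sampling time point". SAP 5.1 and 5.2 plan noncompartmental parameters for cohorts 1 and 2 only.

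SAP 5.1 defines the accumulation ratio once, without distinguishing cohorts: "Racc will be derived as the ratio of AUCtau,ss from Day 14 divided by the AUCtau from Day 1".

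**The concern.** The listed terms do not produce the listed output. A programmer who follows the text literally will print the same ratio and interval against each dose level, although nothing dose-specific was estimated. The two cohorts differ in both dose and duration, so equal accumulation cannot be taken for granted. If it differs, the reported figure lies between the two true ratios and its interval is centred on neither.

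For cohort 3, one concentration per visit gives neither an area under the curve nor an observed maximum. The AUCtau and Cmax comparison named for that cohort therefore has no data behind it in the visible plan.

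PK is part of the primary objective for cohorts 1 and 2. If this analysis is run, its tables should therefore mean what their labels say.

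**Working it through.** The documents state no accumulation ratio, power or sample size for this model, so there is no figure of theirs to reproduce.

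**1. The day contrast.** The model as written is

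E[log Y] = b0 + b1·I(last PK day) + b2·log(dose).

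At dose d, the last day minus Day 1 is (b0 + b1 + b2·log d) − (b0 + b2·log d) = b1. Dose cancels, so exp(b1) is the same at 3 mg and 6 mg. This is algebra and rests on no assumed value.

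**2. Check by fitting.** Simulated data with 6 active patients per cohort, assumed true ratios 1.2 and 2.0, between-subject log-SD 0.3 and residual log-SD 0.05, fitted by REML:

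| Model | 3 mg (cohort 1) | 6 mg (cohort 2) |
|---|---|---|
| Observed geometric mean ratio | 1.19 | 2.04 |
| As written | 1.56 (90% CI 1.36 to 1.78) | 1.56 (same CI) |
| With day × log-dose | 1.19 | 2.04 |
| Day with separate levels 1, 7, 14 | 1.19 (Day 7) | 2.04 (Day 14) |

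A separate fit within one cohort has three design columns (intercept, day, log-dose) but rank 2. Log-dose is constant there, so its coefficient cannot be estimated.

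**3. Size of the pooling error.** With equal cohort sizes and complete pairs, the common ratio estimates the geometric mean of the two cohort ratios. Assumptions, not from the documents: cohort 1 ratio 1.2; cohort 2 ratio R2 from 1.2 to 2.0; residual log-SD 0.2, 0.3 or 0.4. The number of active patients, 6 per cohort, is from the protocol. Common ratio = √(1.2 × R2); for example √(1.2 × 1.6) = √1.92 = 1.39.

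Coverage comes from 200,000 simulated data sets per scenario. The pooled interval uses the 12 paired log-differences (t, 11 df). Between-subject variance cancels in the pairs.

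| R2 | Common ratio | Coverage, SD 0.2 | SD 0.3 | SD 0.4 |
|---|---|---|---|---|
| 1.2 | 1.20 | 90% | 90% | 90% |
| 1.3 | 1.25 | 87% | 89% | 89% |
| 1.4 | 1.30 | 79% | 85% | 87% |
| 1.6 | 1.39 | 58% | 74% | 80% |
| 2.0 | 1.55 | 26% | 50% | 64% |

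Coverage is the same for either cohort's true ratio. With cohort-specific means and a pooled variance (t, 10 df), it is 90% in all 15 scenarios.

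**4. Cohort 3.** SAP 5.2.1 asks for AUCtau and Cmax on Day 28 and Day 1. SAP 5.1, protocol 8.5 and the Table 8-1 footnote supply a single 15-minute concentration per visit. From that, only a ratio of 15-minute concentrations can be estimated. SAP 5.1 leaves room for further PK parameters in any cohort, but that supplies no further samples.

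**5. Racc.** SAP 5.1 uses only Day 14 in the numerator. Cohort 1's last profile is on Day 7, so the definition does not apply to that cohort, whereas SAP 5.2.1 uses Day 7 for it.

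**The case against.** The strongest reply is that the combined Day 7/14/28 level is shorthand for each cohort's own last PK day. The section opens by naming the three contrasts separately. If day were coded with distinct levels, the model would give a ratio for cohort 1 and another for cohort 2 with no interaction, as the last row of the first table shows. That reading is possible, but it is not what is written: the factor is given two named levels. Separate fits per dose level would also work, but they make the stated log-dose covariate redundant. The SAP states neither option, so the text needs correcting whichever was meant.

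The coverage figures apply only to the pooled reading and depend on assumed ratios and SDs. Nothing in the documents shows that accumulation differs between cohorts. If it does not, the pooled ratio is right and more precise; at R2 = 1.3 coverage is still 87% to 89%.

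The consequence is also small, and this stands. The analysis is exploratory and optional. Individual PK parameters are still listed and summarised, so a divergence between cohorts would be visible. Cohort 2 may be skipped, in which case only one dose has AUCtau and Cmax and nothing is pooled.

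For cohort 3, redacted text might justify using the 15-minute value as a stand-in for the peak, but the readable text defines no such surrogate.

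**Conclusion.** The concern holds. With the terms SAP 5.2.1 lists, the day effect is a single ratio and cannot be the dose-level result the section promises. The cohort 3 request for AUCtau and Cmax conflicts with the visible sampling schedule. The Racc definition is a related drafting slip.

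The structural point needs no assumptions. The size does: it is zero if the two cohorts accumulate equally, and under the assumed inputs the worst case is coverage of 26% (ratios 1.2 and 2.0, residual log-SD 0.2). The effect is confined to this optional exploratory analysis. The descriptive PK summaries and the cohort 3 FEV1 analysis are unaffected, and the documents do not show that this model drives dose selection. It should be corrected, but it does not threaten the trial's main conclusions.

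**What to change.** Revise the SAP as follows.

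1. **Section 5.2.1, cohorts 1 and 2.** Use fixed effects for cohort (dose level), day (Day 1, last PK day) and day-by-cohort, with subject random; or analyse paired log-differences within each cohort. Report Day 7/Day 1 for cohort 1 and Day 14/Day 1 for cohort 2, each with a 90% CI. Label each ratio by cohort and day, because dose and duration change together and a difference between cohorts cannot be attributed to dose alone.
2. **Section 5.2.1, cohort 3.** Drop AUCtau and Cmax. Analyse the 15-minute concentration only, comparing Day 28 with the first dosing day of the QBW276 period (Visit 106 with 101, or Visit 205 with 201).
3. **Section 5.1.** Define Racc as Day 7/Day 1 for cohort 1 and Day 14/Day 1 for cohort 2.

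This is wording only and needs no new data. The cost is precision, since each ratio rests on 6 patients. When the true ratios are equal, the log-scale half-width is about 1.42 times that of the pooled model (√2 × 1.812/1.796 = 1.43 at a common SD, and 1.42 on average in simulation). Typical limits are then a factor of 1.22 either side instead of 1.15 at residual log-SD 0.2, or 1.50 instead of 1.33 at 0.4. The penalty shrinks as the ratios diverge.
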